### 3.2 Schedule of Visits and Assessments

The schedule of visits and assessments along with study design schema is provided below.

**Figure 1. Schedule of Visits and Procedures**

Visit 	Screening Visit 	Baseline Visit 	Week 2 	Week 4 	Week 8/Exit 
Visit Window (Days)	Day -8 to -1	Day 1	Day 14 ± 3	Day 28 ± 3	Day 56 ± 3
Visit Sequence Number	1	2	3	4	5
Informed Consent	X				
Inclusion/Exclusion	X	X			
V-FUCHS Questionnaire		X		X	X
Demography	X				
Medical/Ophthalmic History	X	X			
Concomitant Medications	X	X	X	X	X
HR/BP	X	X			X
Urine Pregnancy Test 			X		X
Ocular Symptoms/AEs	OU	OU	OU	OU	OU
BCVA (ETDRS protocol)	OU	OU	OU	OU	OU
Biomicroscopy	OU	OU	OU	OU	OU
Ultrasound Pachymetry (CCT) 	OU	OU	OU	OU	OU
IOP	OU	OU	OU	OU	OU
Dilated Ophthalmoscopy	OU				OU
Undilated Ophthalmoscopy		OU	OU	OU	
Tomography (Pentacam®) 	OU	OU	OU	OU	OU
SE Determination  and Randomization			X		
Eye Drop Instruction and Demonstration			SE		
Dispense Study Medication			X		X

Abbreviations: AEs = adverse events; BCVA = best corrected visual acuity; BP = blood pressure; CCT = central corneal thickness; ETDRS = Early Treatment Diabetic Retinopathy Study; HR = heart rate; IOP = intraocular pressure; OU = both eyes; SE = Study Eye; V-FUCHS = Visual Function and Corneal Health Status

 Subjects should be scheduled at approximately the same time of day ± 60 mins in the morning (ideally at or before 10:00 AM local time) for each visit

[figure not shown]
 Required only for females of childbearing potential

 Ultrasound pachymetry should be performed at approximately the same time of day ± 60 mins and always before noon local time

 Selected sites only, may be completed prior to ophthalmoscopy at the Screening and Week 8/Exit Visit while the subject is dilating

 Please refer to Section 4.4 for instructions on study eye determination

**Figure 2. Study Design Schema**

\* Any subject randomized to netarsudil QD who, in the opinion of the Investigator, has not responded adequately to treatment, may have their netarsudil dosing frequency increased to BID for the remainder of the study.

† Study eye only. AM dosing should occur between 06:00 and 09:00 hours. PM dosing should occur between 19:00 and 22:00 hours.

‡ Subjects randomized to the netarsudil QD dosing regimen will be instructed to instill one drop of the Study Artificial Tear in their study eye every morning, and one drop of netarsudil in their study eye every evening.

## 4. Study Treatments

### 4.1 Treatment Administered

Subjects will be randomized using a 1:1 allocation ratio to one of two treatment groups:

- Netarsudil QD Dosing Regimen
  - Study Artificial Tear: one drop in the study eye in the morning
  - Netarsudil 0.02% ophthalmic solution: one drop in the study eye in the evening
- Netarsudil BID Dosing Regimen
  - Netarsudil 0.02% ophthalmic solution: one drop in the study eye in the morning and in the evening

Doses will be self-administered by the study subjects. If the subject is using any another topical ophthalmic drop (e.g., ocular hypotensive medications) at the same time as netarsudil, the subject should be instructed to instill netarsudil first, and wait at least 15 minutes before instilling any additional drops.

For subjects deemed unable to self-administer the doses, a caregiver will be asked to administer the medication. All subjects will administer study medication for approximately 8 weeks.

### 4.2 Method of Assigning Patients to Treatment Groups

Subjects will be assigned to treatment groups through the use of an interactive response technology (IRT) system. Subjects will be identified by subject ID (xxx-xxx) with 3 digits for site ID followed by 3 digits for subject number in all datasets and listings for this study.

### 4.3 Masking and Unmasking

This is an open-label study, therefore masking and unmasking procedures do not apply.

## 5. Sample Size and Power Considerations

This study is not powered to detect a pre-stated efficacy signal, but rather will be used to inform the design and power for any possible future studies. With a sample size of up-to 20 subjects per treatment group, the precision of the point estimate of mean change from baseline in CCT, as measured by the half-width of the two-sided 90% confidence interval (CI), will be approximately  $1/2.7$  of the standard deviation (SD) of the change from baseline, yielding 90% confidence that the true mean change from baseline is within  $\pm SD/2.7 \mu\text{m}$  of the observed mean change from baseline. That is, if the SD of the change from baseline is  $60 \mu\text{m}$ , then the half-width of the two-sided 90% CI would be  $60 \mu\text{m} \times 1/2.7 = 22.2 \mu\text{m}$ , yielding 90% confidence that the true mean change from baseline is within  $\pm 22.2 \mu\text{m}$  of the observed mean change from baseline.

With a sample size of up-to 20 subjects within a treatment group, the study will have 80% power to reject  $H_{01}$  or  $H_{02}$  and in favor of  $H_{11}$  or  $H_{12}$  respectively and demonstrate a statistically significant mean change from baseline, assuming the true effect size (mean change / SD) is 0.577 or larger (e.g. assuming the true mean change from baseline is  $34.6 \mu\text{m}$  and the SD is  $60 \mu\text{m}$ ), a one sample t-test and a two-sided alpha = 0.10.

With a sample size of up-to 20 subjects per treatment group, the study will have 95% confidence of ruling out AEs with true incidence rates of 13.9% or higher within each treatment group. That is, with up-to 20 subjects in a treatment group, if an AE of a specific type is not observed, then with 95% confidence, the true incidence rate of that adverse event is less than 13.9%.

Similarly, with a sample size of up-to 40 subjects combined over treatment groups, the study will have 95% confidence of ruling out AEs with true incidence rates of 7.2% or higher within each treatment group. That is, with up-to 40 subjects in a treatment group, if an AE of a specific type is not observed, then with 95% confidence, the true incidence rate of that AE is less than 7.2%.

## 6. Data Preparation

### 6.1 Input Data

Study data will primarily be recorded on the electronic case report form (eCRF) supplied by Statistics & Data Corporation (SDC) using electronic data capture (EDC) system, iMednet™. The only external data source is the site level protocol deviations that will be collected separately at site and will be transferred to SDC from Aerie. It will be combined with the protocol deviations in EDC by SDC for the final deviation classification by Aerie.

When all prerequisites for database lock have been met, the database will be locked. Any changes to the database after data have been locked can only be made with the approval of the Sponsor in consultation with SDC.

Final analysis will be carried out after the following have occurred:

- Database lock has occurred, including receipt of all final versions of external vendor data, with written authorization provided by appropriate SDC and Sponsor personnel
- Protocol deviations have been identified and status defined (major/minor deviations)
- Analysis populations have been determined

### 6.2 Output Data

Data from EDC will be transferred to SDC Biostatistics and will then be mapped to analysis datasets (ADs). Raw data will be used to create the subject listings along with ADs as needed, while all tables will be based on the ADs.

## 7. Analysis Populations

A total of approximately 40 subjects will be enrolled into the study at approximately 20 investigational sites within the United States. Subjects will be at least 18 years of age with a diagnosis of FCD, each of whom should meet all of the inclusion criteria and none of the exclusion criteria.

### **7.1 Modified Intent-to-Treat (mITT) Population**

The mITT population will include all randomized subjects who have received at least one dose of study medication. This population will be the primary population for efficacy analyses and will be used to summarize a subset of efficacy variables and will summarize subjects as randomized.

### **7.2 Per Protocol (PP) Population**

The PP population is a subset of the mITT population, which will include those subjects (and their visits) who do not have major protocol deviations likely to seriously affect the primary outcome of the study. This population will be the secondary population for efficacy analyses and will be used to summarize a subset of efficacy variables. If the PP and mITT populations are exactly the same, then additional efficacy analyses on the PP population will not be performed. The PP population will summarize subjects as treated.

### **7.3 Safety Population**

The safety population will include all randomized subjects who have received at least one dose of investigational product. This population will be used to summarize safety variables and will summarize subjects as treated.

## **8. General Statistical Considerations**

### **8.1 Unit of Analysis**

Safety endpoints will be analyzed for both eyes. For efficacy endpoints, the primary unit of analysis will be the study eye defined based on CCT of at least 600  $\mu\text{m}$  evaluated by ultrasound pachymetry. If both eyes qualify based on CCT and enrollment criteria, the study eye will be the eye with the thinner cornea at the baseline. If both eyes have the same CCT, the study eye will be the right eye. Qualified fellow eyes will also be summarized. A qualified fellow eye for a given subject is a fellow eye that also met all of the inclusion criteria and none of the exclusion criteria at the Screening and Baseline Visits.

### **8.2 Missing or Inconclusive Data Handling**

#### **8.2.1 ASSESSMENT WINDOWS**

Assessment window mapping will be applied to both efficacy and safety outcomes for table summaries using observed data only (ODO). Unscheduled or early termination visits that are within the protocol specified window of a scheduled visit will be mapped to that visit to replace the missing scheduled visit. Missing data handling for efficacy variables as described in Section 8.2.2 will be applied after assessment window mapping. Both the actual visit and windowed visit will be displayed in the listings.

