6.10.2 Non-completing Subject

A non-completing subject is defined as one who exits the study by their own volition or at the discretion of the Investigator, the Medical Monitor, and/or an Aerie Safety Officer/designee. Any subject may decide to voluntarily withdraw from the study at any time without prejudice. If discontinuation of treatment is necessary, the Investigator will make every attempt to complete all subsequent safety assessments listed for the Week 8 / Early Termination Visit.

The subject may also be discontinued from the study for the following reasons:

- AEs (including intercurrent diseases reported by the subject or observed by the Investigator with documentation on the CRF)
- Withdrawal of Consent
- Non-compliance (e.g., non-adherence to scheduled follow-up visits or use of study treatment)

- Lost to Follow-up
- Pregnancy
- Investigator Decision
- Protocol Deviation
- Death
- Other

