7.2.2 Week 2 (Day 14 \pm 3) Procedures

- Concomitant medication review
- Ocular symptoms and AE review for both eyes
- BCVA using the ETDRS method and following manifest refraction for both eyes
- Anterior segment biomicroscopic examination of both eyes
- CCT will be measured by ultrasound pachymetry in both eyes
 - Note: Ultrasound pachymetry should be performed at approximately the same time of day for all visits (\pm 60 minutes) and always before noon (local time)
- IOP in both eyes
- Ophthalmoscopy without dilation in both eyes
- Tomography (Pentacam[®]) for both eyes (at selected sites only)

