#### **13.4 Intraocular Pressure**

IOP will be collected at all scheduled visits for both eyes using an Applanation Tonometer. Two or three results (when IOP difference between test 1 and test 2 is more than 2 mmHg in one or both eyes) will be collected for both eyes. Mean IOP (mean when two results are collected or median IOP when three results are collected) will be calculated and summarized. The mean IOP and change from baseline mean IOP will be summarized for each eye (study eye and fellow eye) using continuous summary statistics by visit for each treatment group. A subject listing of IOP will also be provided.

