#### **13.6 Vital Signs**

Vital signs (heart rate, systolic sitting blood pressure, diastolic sitting blood pressure) will be collected at Screening, Baseline and Week 8. The results will be summarized by visit for each treatment group, using continuous summary statistics, including change from baseline. A subject listing of the vital signs results will also be provided.

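### Exit and unscheduled safety exams that fall outside the ±3-day visit windows, or have no missed visit to replace, reach only the listings, because no last-value or worst-value safety row is planned

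*SAP*

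**What the plan says.** SAP 8.2.1 states that "Assessment window mapping will be applied to both efficacy and safety outcomes" in the observed-data tables. An early-termination or unscheduled visit must meet two conditions. It must lie in a protocol window ("Unscheduled or early termination visits that are within the protocol specified window of a scheduled visit will be mapped to that visit"), and it must serve "to replace the missing scheduled visit". The section adds that listings show both the actual and the windowed visit. It does not say how an exam that meets neither condition, or only one, is tabulated.

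The windows come from Protocol Table 1 and Sections 7.2.2 to 7.2.4: Day 14, Day 28 and Day 56, each ±3 days. Early termination shares the Week 8 procedure list.

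The protocol asks sites for these exams. Under Section 6.10.2, if treatment has to stop, "the Investigator will make every attempt to complete all subsequent safety assessments listed for the Week 8 / Early Termination Visit". Section 6.10.3 asks for a final visit with the full set of examinations after withdrawal of consent or non-compliance.

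On the analysis side, SAP 13.2 and 13.4 summarize BCVA and IOP "using continuous summary statistics by visit for each treatment group". SAP 13.3 and 13.5 give biomicroscopy and ophthalmoscopy shifts for each follow-up visit, and 13.3 also splits the biomicroscopy counts by visit. Vital signs, under 13.6, "will be collected at Screening, Baseline and Week 8". The table list in SAP 18 has no last-value, worst-value or early-termination safety table.

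**The concern.** Sites are asked to examine subjects who leave early, but the SAP gives many of those exams no table row. Safety is a stated secondary objective, and a subject who stops because of intolerance or corneal worsening may show the relevant finding first, or most clearly, at the exit exam. A by-visit table that holds only exams in or mapped to scheduled visits would not show it.

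The SAP treats efficacy differently. Under 8.2.2, LOCF draws on scheduled, unscheduled and early-termination visits, and withdrawals for adverse events or lack of efficacy receive the worst post-baseline value in the imputation analysis. The safety exams have no counterpart to either.

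**Working it through.** The documents state no figure for window coverage, so this is a direct count.

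**Inputs.** Windows (Protocol Table 1): Week 2 = Days 11-17, Week 4 = Days 25-31, Week 8 = Days 53-59. Possible exit days before the Week 8 window opens: Days 2-52. Arm size: up to 20 (SAP 5).

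**Days in no window.**
- Days 2-10: 9 days. Days 18-24: 7 days. Days 32-52: 21 days.
- Uncovered: 9 + 7 + 21 = 37. Covered: 7 + 7 = 14. Total: 51.
- 37/51 = 72.5% of calendar days.
- Extending the range to Day 56 gives 37/55 = 67.3%; to Day 59, 37/58 = 63.8%.

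**Effect of the second condition.** Suppose earlier scheduled visits took place on Days 14 and 28. An exit exam later in the same window then has nothing to replace. Only Days 11-13 and 25-27 still map, which is 6 of 51, leaving 45/51 = 88.2% unmapped. If an exit exam on Day 14 or 28 is itself taken as the scheduled visit, the figures are 8 mapped and 43/51 = 84.3% unmapped.

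Example: a subject attends Week 4 on Day 27 and leaves on Day 30. The Day 27 exam is tabulated. The Day 30 exam is not.

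**Vital signs.** Week 8 is the only scheduled post-baseline measurement, so none of Days 2-52 leads to that row.

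**Possible number of exams.** Assuming that 5%, 10% or 20% of 40 subjects leave early, at evenly spread times (an assumption, since the documents give neither figure):
- 2 × 37/51 = 1.5
- 4 × 37/51 = 2.9
- 8 × 37/51 = 5.8

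**Effect of one omitted subject with a grade increase, n = 20.**
- Fixed denominator: 1/20 = 5.0 points.
- Observed-data denominator, with k other subjects showing an increase: (k+1)/20 − k/19 = (19 − k)/380.
- k = 0: 19/380 = 5.0 points. k = 5: 14/380 = 3.7 points. k = 10: 9/380 = 2.4 points.

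**The case against.** The strongest reply is that leavers remain visible elsewhere. Adverse-event tables are not by visit. They cover events leading to discontinuation of study medication, maximum severity and relationship (SAP 13.1). Disposition tabulates reasons for leaving (SAP 9). A leaver's earlier scheduled exams stay in the by-visit tables, and every record of about 40 subjects is listed. An exit exam on Days 11-17 or 25-31 that replaces a missed visit is kept, apart from vital signs. All of this stands, and it limits the loss to exam findings at exit.

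It is also fair that keeping a Day 12 blood pressure out of a Week 8 row is correct by-visit reporting. The gap is the lack of any other row, not the mapping itself.

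A reader might infer three stronger things that the documents do not support.

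- That 73% of exit exams are lost. The figure counts days, not visits, and exits may cluster at scheduled visits.
- That the safety summaries are biased favorably. Subjects also leave through withdrawn consent, loss to follow-up or non-compliance. Exit exams may be off drug, and netarsudil lowers IOP, so the direction is plausible for some measures and unclear for others.
- That each omitted subject is always worth 5 points. That needs a fixed denominator of 20, which SAP 13.3 does not state, or no other case.

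Finally, a programmer might place every exit exam under the shared Week 8/Exit label. Section 8.2.1 permits that only on Days 53-59, so the label does not close the gap.

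**Conclusion.** The point holds for exam-based safety tables. Followed as written, SAP 8.2.1 and 13 leave in the listings alone any exit or unscheduled exam on the 37 of Days 2-52 outside the windows, and any in-window exam whose scheduled visit was attended. For vital signs, no reading before Day 53 enters the one post-baseline row.

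The exclusion is the effect of the rule; no sentence states it. How many exams are affected depends on dropout rate and timing, which are not given. The direction of any bias depends on why subjects leave. One omitted subject with a grade increase is worth up to 5 points at n = 20, or about 2.4 to 5.0 points with an observed-data denominator when 0 to 10 others have an increase.

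The primary CCT analysis does not depend on this point. It is a worthwhile, inexpensive improvement to safety reporting.

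**What to change.** Keep SAP 8.2.1 for the by-visit rows and amend SAP 13 as follows.

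1. Add a last-post-baseline-assessment row to Tables 14.3.3.1 to 14.3.3.5.
2. Add an any-post-baseline (worst) row to Tables 14.3.3.2.2 and 14.3.3.2.3.
3. Build both rows from all scheduled, unscheduled and early-termination exams, regardless of window.
4. For subjects who switch from QD to BID, attribute each exam to the regimen taken at that exam. Pre-switch exams go to QD; post-switch exams go to BID or to a separate QD-to-BID group, in line with the handling of adverse events in SAP 13.1. Without this, a Week 2 finding on QD could be counted under BID, because SAP 13 moves switchers to BID at Week 8.
5. Footnote that the added rows mix exposure durations and may include off-drug exams.

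The cost is SAP wording and one row per table. No new data are needed. The drawback is the mixed exposure, which the footnote discloses.

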#### **8.2.2 MISSING DATA HANDLING FOR EFFICACY VARIABLES**

The primary analysis will be completed with available data per subject from the mITT population.

Robustness analyses will also be presented based on the multiple imputation (MI) methodology under different assumptions of missingness and intercurrent events, using last observation carried forward (LOCF), and using the PP population with available data per subject. Imputation using MI or LOCF will

only be performed on study eye missing data at post-baseline scheduled visits. No imputation will be performed for missing fellow eye data and unscheduled post-baseline visits.

Intercurrent events will be primarily handled in the following manner:

1. Discontinuation of study medication and non-optimal compliance will be ignored, values measured after discontinuation of study medication or regardless of compliance will be used in the analyses [treatment policy strategy].
2. Withdrawal due to lack of efficacy or AEs: missing data will be singly imputed as the worst within subject observation prior to the intercurrent event [hypothetical strategy]. For efficacy variable CCT, the worst is the maximum within subject observations. In addition, the worst observation should come from post-baseline scheduled and unscheduled visits prior to the intercurrent event.
3. Missing data without withdrawal or withdrawal due to reasons other than lack of efficacy or AEs: missing data will be imputed employing MI fully conditional specification (FCS) regression method.

For the LOCF imputation, only the observations from post-baseline visits including scheduled, unscheduled, and early termination visits for a given subject will be carried forward.

### **8.2.3 MISSING DATA HANDLING FOR PARTIAL MISSING DATES**

In general, there will be no imputation of missing dates other than for partial or missing dates where complete dates are required to flag data as treatment-emergent or concomitant with treatment. Partial/missing start and end dates for AEs and concomitant medications will be imputed as follows:

Partial/missing start date:

- Dates with missing day only will be imputed as the 1st of the month unless the month and year are same as the month and year of first dose of study medication, in which case missing day will be imputed as the first dose day of study medication.
- Dates with both day and month missing will be imputed as 1 Jan unless the year is same as the year of first dose of study medication, in which case missing day and month will be imputed as the first dose day and month of study medication.
- Completely missing dates will be imputed as the first dose date of study medication unless the end date is on or before the first dose date of study medication, in which case missing date will be imputed as 1 Jan of the same year as the end date.

Partial/missing end date:

- Dates with missing day only will be imputed as the last day of the month unless the month and year are the same as the month and year of the last dose of study medication, in which case missing day will be imputed as the last dose day of study medication.

- Dates with both day and month missing will be imputed as 31 Dec unless the year is same as the year of the last dose of study medication, in which case missing day and month will be imputed as the last dose day and month of study medication.
- If the ongoing flag is missing or “Yes” then the date will not be imputed unless death date is available, in which case the missing date will be imputed as the death date. If ongoing is “No” then the missing end date will be imputed as the last dose date.
- If the imputed date is after the date of death, then the end date will be set equal to the date of death.

The original dates will be displayed in data listings and the imputed dates will be used in derivations only (study day, treatment-emergence status, prior or concomitant medication etc).

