### 13.1 Adverse Events

An AE is defined as any untoward medical occurrence associated with the use of a drug in humans, whether or not the event is considered drug-related. An AE can therefore be any unfavorable and unintended sign (eg, an abnormal laboratory finding), symptom, or disease occurring after the first dose of study drug, without any judgment about causality. Any pre-existing medical condition that worsens after first administration of the study drug will also be considered a new AE. The AE reporting period starts from the time the subject signs the informed consent until the subject's last study visit. All AEs will be coded using MedDRA Version 23.0.

A treatment-emergent adverse event (TEAE) is defined as any event that occurs or worsens on or after the first dose of study medication. Adverse events recorded on the eCRF which began prior to treatment and remained unchanged or improved will not be included in the summary tables but will be included in the AE data listings. For all AE summary tables, a third group other than QD and BID dose group will be presented to capture the AEs for those subjects who switched the treatment dose from QD to BID starting from Week

4. The AE that began on or after the switch will be considered treatment emergent to the BID treatment; The AE that began before the switch and continued after the switch will be considered treatment emergent to the QD treatment only; if the AE worsened on or after the switch, the new AE (one with higher severity) would become a TEAE for the BID dose and the original AE would be treatment emergent to the QD dose.

An overall summary will be presented that includes the number of events and the number and percentage of subjects who experienced at least one TEAE, by treatment group. This summary will also include breakdowns of TEAEs further categorized as ocular (study eye and fellow eye separately with TEAEs occurred on both eyes counted towards study eye once and fellow eye once) or non-ocular, TEAEs by maximum severity, TEAEs by maximum relationship to study medication, TEAE by expectedness, serious TEAEs, TEAEs leading to study medication discontinuation, TEAEs leading to death.

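### Partial adverse-event start dates are imputed without reference to the Week 4 switch, so some events that began after a move from QD to BID are labelled QD

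*SAP*

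**What the plan says.** SAP 8.2.3 gives three rules for an incomplete AE start date.

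- **Day missing.** The rule opens "Dates with missing day only will be imputed as the 1st of the month unless the month and year are same as the month and"; here the comparison is with the first dose and, on a match, an exception applies: "in which case missing day will be imputed as the first dose day of study medication".
- **Day and month missing.** 1 January, unless the year is that of the first dose, "in which case missing day and month will be imputed as the first dose day and month of study medication".
- **Whole date missing.** The first-dose date, unless the event ended on or before that date.

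The section adds that "imputed dates will be used in derivations only (study day, treatment-emergence status, prior or concomitant medication etc"). The original dates stay in the listings.

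SAP 13.1 covers subjects moved from QD to BID at Week 4. "For all AE summary tables, a third group other than QD and BID dose group will be presented to capture the AEs" of these subjects. Within them, onset decides the regimen: "The AE that began on or after the switch will be considered treatment emergent to the BID treatment", whereas "The AE that began before the switch and continued after the switch will be considered treatment emergent to the QD treatment only". If an AE worsens on or after the switch, the higher-severity record counts towards BID.

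Neither document has a rule for a partial date that could lie on either side of the switch.

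**The concern.** The anchors in SAP 8.2.3 suit a single question: did the event start before or after the first dose? Pulling an uncertain date towards the first dose is the cautious choice there, because doubtful events are kept as treatment-emergent. SAP 13.1 asks the same imputed date a second question: which regimen was the subject on? For that question the anchors pull one way, towards QD.

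The mislabelling can occur even when the study's own records show otherwise. Suppose first dose is on 10 March and the switch on 6 April (Day 28). An AE absent at the Week 4 review is reported at Week 8 with a start recorded only as April. It is imputed to 1 April and labelled QD only.

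Safety of each regimen is a secondary objective (Protocol 2.2), and Protocol 3.2 describes the optimal regimen partly by minimal adverse effects. The switchers are the only subjects observed on both frequencies, so the before/after split of their events should be right.

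**Working it through.** The plan states no mislabelling rate, so there is no figure to reproduce. The check applies the SAP rules directly.

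**Inputs**

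- Switch at Week 4, Day 28 ± 3 (Protocol 7.2.3); its date is taken as the Week 4 visit date.
- Exit at Week 8, Day 56 ± 3 (Protocol 7.2.4).
- First dose on Day 1, the dispensation date (SAP 8.3).
- Imputation rules from SAP 8.2.3; labelling rule from SAP 13.1.
- Assumption, not in the documents: AE onset is uniform from switch to exit.

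**Day missing, one subject**

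Let L = exit day − switch day + 1 = 56 − 28 + 1 = 29 possible onset days. Let d be the number of these that lie in the calendar month of the switch, with d = 0 if the switch is on the 1st. Onsets on those d days are imputed to the 1st, or to the first-dose day if that is the same month. Either is before the switch, so the label is QD. Onsets in a later month are imputed to the 1st of that month, after the switch, and stay BID. The mislabelled share is d / L.

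| First dose | Switch (Day 28) | Exit (Day 56) | d / L | Share |
|---|---|---|---|---|
| 1 March | 28 March | 25 April | 4/29 | 13.8% |
| 5 March | 1 April | 29 April | 0/29 | 0% |
| 6 March | 2 April | 30 April | 29/29 | 100% |
| 10 March | 6 April | 4 May | 25/29 | 86.2% |
| 15 March | 11 April | 9 May | 20/29 | 69.0% |
| 20 March | 16 April | 14 May | 15/29 | 51.7% |

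**Day missing, average**

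In a 30-day month with the switch equally likely on any day s, d = 31 − s for s = 2 to 30 and d = 0 for s = 1. The sum is 29 + 28 + … + 1 = 435. The mean is 435/30 = 14.5 days, and 14.5/29 = 50.0%. Enumerating all 365 first-dose dates of 2021 gives 50.7%; first doses from September 2020 to August 2021 give the same.

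**Sensitivity of the average**

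| Scenario | Labelled QD |
|---|---|
| Day 28 to Day 56, uniform onset | 50.7% |
| Switch Day 25, exit Day 59, uniform | 42.1% |
| Switch Day 31, exit Day 53, uniform | 60.5% |
| Onset rising linearly after the switch | 35.4% |
| Onset falling, half-life 14 days | 61.7% |
| Onset falling, half-life 7 days | 70.8% |

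**More of the date missing**

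With day and month missing and the event in the first-dose year, the imputed date is the first-dose date, so 100% are labelled QD. Averaged over all start dates, including those that cross a year end, it is about 96%. With the whole date missing, a post-switch event cannot have ended by the first dose, so the first-dose date applies and again 100% are labelled QD.

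**The opposite error**

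In the same enumeration, no missing-day AE that began before the switch was imputed to the switch date or later (0 events).

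**The case against.** **Rarity.** The error needs a QD subject who switched and who then has an AE with an incomplete start date. Protocol 6.9.1 asks for start and stop dates, AEs are reviewed at every visit, data omissions are queried (Protocol 10.11), and source verification covers AEs (Protocol 10.6). Post-switch follow-up is only about four weeks. All of this stands. The documents give neither the number of switchers nor the number of partial dates, so no absolute effect can be computed.

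**Presentation.** A reader might infer that the BID arm will look safer and the QD arm less safe. The documents do not support that. Switchers have their own group in every AE summary table, and the AEs of subjects randomized to BID are not re-dated across a switch. SAP 13.1 does not make clear whether a switcher's QD-labelled event appears in the QD column or within the third group, so the column affected cannot be named. What remains is a shift from the post-switch BID label to QD within switchers.

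**Size per event.** With at most 20 QD subjects, a reader might infer that each misplaced event moves a column by at least 5 percentage points (1/20). That does not follow. SAP 13.1 counts a subject once per preferred term and once per system organ class, so an event may add nothing to a row already counted. The denominator for the third group is also not stated.

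**Use of the result.** AE summaries are descriptive, and no rule selects a regimen from them. That is correct, and it limits the consequence. It does not reconcile the two SAP sections.

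**Conclusion.** The point holds as a minor inconsistency between SAP 8.2.3 and SAP 13.1. Followed exactly, the rules give some post-switch AEs the wrong regimen label, and the error runs only towards QD. It is more than missing detail, because a stated rule produces the wrong label.

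Under uniform onset with a Day 28 switch and Day 56 exit, about 51% of post-switch AEs with only the day missing are affected. The range is 42–61% across visit windows and 35–71% across the onset patterns tried; for one subject it can be anything from 0% to 100%, depending on where the switch falls in the month. It is 100% when day and month are missing in the first-dose year or the whole date is missing. These are shares of incomplete post-switch dates among switchers, not shares of all AEs. The absolute number is unknown and probably small.

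**What to change.** Add to SAP 8.2.3: for subjects moved from QD to BID whose known date parts allow onset on either side of the switch, an AE not reported at or before the Week 4 AE review is imputed to the switch date; otherwise the current rule applies. Using the switch date itself matches the boundary in SAP 13.1.

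Imputing every switch-month event to the switch date would not do. It removes the error above but moves about 54% of pre-switch missing-day AEs to BID (Day 28 switch, uniform onset). The visit of first report is what separates the two cases.

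That visit is not among the AE items listed in Protocol 6.9.1 and 6.9.2, so the sponsor should confirm that it can be retrieved. If it cannot, report the number of AEs whose side of the switch is undetermined and show the table under both assignments.

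The cost is a short addition to the SAP and a little programming, with no new subject procedures. The drawback is that an event which began before Week 4 but was recalled only later could be labelled BID.
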